Effectiveness, medical costs, and QALYs: Few HIV prevention studies are sufficiently powered to directly measure reductions in infections, and we will estimate HIV incidence among sexual and injection-drug-using partners under the standard of care scenario and under the intervention scenario using Bernoulli process models¹¹⁶ of injection drug use and sexual intercourse with behavioral patterns based on participant assessments and HIV transmission probabilities based on an updated review of the literature. The model will be based on participant data with a one-year timeframe for intervention costs and HIV transmission, and we will incorporate literature-based estimates of lifetime treatment costs and QALYs associated with new HIV infections in Ukraine, discounted at 3% per annum.^{111,117} Differences between the scenarios in estimated HIV transmission are expected to be driven primarily by ART use, but we will also incorporate observed data on intercourse, condom use, injection drug use, syringe sharing, and partner characteristics. The primary model will be based on the point estimates of parameters, but we will also conduct sensitivity analyses where input parameters are sampled from distributions that capture the uncertainty in our estimates. Many modeling approaches are available for modeling the incremental cost-effectiveness of D2C; given the exploratory nature of the proposed research, we believe a Bernoulli process model is appropriate.

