Incremental cost-effectiveness and threshold analyses: The cost-utility ratio will be computed based on the estimation of net incremental cost (i.e., difference between the incremental intervention costs and the incremental HIV treatment costs averted) divided by the QALYs averted. For a given model run, intervention will be considered: cost-saving if the incremental intervention cost is less than the incremental treatment cost averted; cost-effective if the net incremental cost per QALY saved is less than society’s willingness to pay to save one QALY; and not cost-effective if net incremental cost per QALY is greater than society’s willingness to pay.¹¹¹ The proportion of model runs that are cost-effective or cost-saving will be used to characterize the probability that the intervention meets these thresholds. We will also use one-way sensitivity analyses to identify conditions under which the intervention would be 90% likely to be cost-effective or cost-saving, such as specific intervention cost thresholds and intervention effectiveness thresholds.

Adverse events (including suicide risk)

The question 9 in PHQ-9 instrument may indicate suicidal thoughts among participants (“Thoughts that you would be better off dead or of hurting yourself in some way”). In case the participant responds anything except “not at all”, Interviewer asks an additional question: “In the last two weeks, have you had any thoughts of hurting yourself in some way?” (not at all, several days, more than half the days, nearly every day). If patient responds “not at all” to this question, the patient denies active suicidal thoughts. He or she is considered “very low or no risk” and no action is triggered at this point. If any other response is received, Interviewer will escort the patient to a clinician in the clinic for a formal assessment of suicide risk according to the national clinical standards (includes an assessment using the Columbia Suicide Severity Rating Scale). For those with a plan, the guidance stipulates that

patients will be transported emergently offsite to a psychiatric inpatient hospital for further evaluation and may be detained against their will for up to 72 hours.

Data management

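### The cost-per-QALY rule for classing model runs sets no condition on the sign of QALYs saved, so dominated runs count as cost-effective and can only inflate the reported probability

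*Combined protocol and SAP*

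**What the plan says.** The section on incremental cost-effectiveness and threshold analyses (Specific Aim 3b) forms a ratio whose numerator and denominator are described as the "difference between the incremental intervention costs and the incremental HIV treatment costs averted) divided by the QALYs averted". Each model run then gets one of three labels:

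- a label that depends on costs alone: "cost-saving if the incremental intervention cost is less than the incremental treatment cost averted";
- a favourable label that depends on the ratio: "cost-effective if the net incremental cost per QALY saved is less than" willingness to pay;
- an unfavourable label that depends on the same ratio: "not cost-effective if net incremental cost per QALY is greater than" willingness to pay.

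The runs come from the preceding section, on effectiveness, medical costs and QALYs. It plans "sensitivity analyses where input parameters are sampled from distributions that capture the uncertainty in our estimates" alongside a primary model based on point estimates.

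The labels are then used twice. First: "The proportion of model runs that are cost-effective or cost-saving will be used to characterize the probability that the intervention meets these thresholds". Second, one-way analyses will "identify conditions under which the intervention would be 90% likely to be cost-effective or cost-saving". The economic sections contain no dominance rule, quadrant rule or net-benefit rule, and none appears elsewhere in the documents.

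**The concern.** A cost-effectiveness ratio can be compared with willingness to pay only when QALYs are gained. When QALYs are lost and net cost is positive, the ratio is negative. It is then smaller than any positive threshold, although the strategy is worse on both counts. The rule as written puts these runs in the favourable class.

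Two outputs are at stake: the probability that D2C is cost-effective or cost-saving, and the cost and effectiveness thresholds at which that probability reaches 90%. The protocol intends the economic results to show under what conditions D2C would be a reasonable investment and whether it could be cost-saving or cost-effective when a full study is planned.

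**Working it through.** The documents state no probability of cost-effectiveness, willingness to pay, cost or QALY value, so there is no planned figure to reproduce.

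**1. The rule applied to one run.** Take net cost +10,000 and QALYs saved −1. The ratio is −10,000. The run is not cost-saving because net cost is positive. It is below any positive willingness to pay and not above it, so its label is cost-effective. With willingness to pay W, net monetary benefit is W × (−1) − 10,000, which is negative for every W > 0.

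**2. Which runs are affected.** In the planned model, lifetime treatment cost (t) and QALYs (q) both attach to new infections. With A infections averted and intervention cost C > 0, net cost = C − A·t and QALYs saved = A·q. If A < 0, net cost is C + |A|·t > 0 and QALYs are −|A|·q < 0. Every run with A < 0 is therefore dominated and mislabelled. The excess in the reported proportion equals P(A < 0).

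**3. How many such runs.** Inputs from the Sample size section: 50% vs 72%, 80 per arm, 2 clinics per arm, between-cluster coefficient of variation 0.15. Assumptions made here: the ART re-engagement difference drives A, and sampling is normal and centred on the pilot's estimate.

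- Independent patients: SE = √[(0.25 + 0.2016)/80] = √0.005645 = 0.075.
- With clustering: SE = √[0.005645 + 0.15² × (0.25 + 0.5184)/2] = √(0.005645 + 0.008645) = 0.1195.

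The share of runs with a negative effect is Φ(−d/SE), where d is the estimated effect:

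| Estimated effect d | SE 0.075 | SE 0.1195 |
|---|---|---|
| +22 points | 0.2% | 3.3% |
| +10 points | 9.2% | 20.1% |
| +5 points | 25.3% | 33.8% |
| 0 | 50.0% | 50.0% |
| −10 points | 90.8% | 79.9% |

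**4. Effect on the reported probability.** This step needs values that the documents do not give. Assumed: 0.10 infections averted per additional patient on ART, t = 5,000, q = 5, W = 3,000, intervention cost 300 per patient. Per patient, net benefit is 3,000 × 0.5d − (300 − 500d) = 2,000d − 300, which is positive only when the sampled effect exceeds 0.15. With SE 0.1195:

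| Estimated effect | Rule as written | Net benefit > 0 |
|---|---|---|
| +22 points | 75.4% | 72.1% |
| +10 points | 53.9% | 33.8% |
| 0 | 60.4% | 10.5% |
| −10 points | 81.7% | 1.8% |

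The levels depend on the assumed values. The gap does not: it is the share in step 3. Under the rule as written, the probability rises as the effect worsens (95.5% at −20 points). It also has a floor: at +5 points it stays at 33.8% however large the intervention cost, while the net-benefit share goes to 0%.

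**5. Effect on the 90% thresholds**, same assumed values. The effectiveness threshold at cost 300 moves from 30.3 to 29.9 points (SE 0.12) and stays at 24.6 (SE 0.075). At cost 100 and SE 0.12 it moves from 20.3 to 14.6 points. The cost threshold at +22 points and SE 0.12 moves from 134 to 174.

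**The case against.** The strongest reply is that a cost per QALY saved presupposes that QALYs are saved, so the rule was never meant for runs that lose them. That reading is fair, but it does not rescue the plan. Such runs would then have no class, and the proportion would depend on whether the analyst drops them, keeps them only in the denominator, or counts them. The section also uses QALYs averted and QALYs saved for the same quantity, so the wording does not settle the sign. The plan cites external recommendations for cost-effectiveness analysis, and analysts may well apply a dominance rule from there. The protocol text itself does not say so.

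Second, the primary economic model uses point estimates, the sampled runs are sensitivity analyses in work described as exploratory, and feasibility of the later trial is judged on the 22% difference in engagement. This stands, and it limits the reach of the point.

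Third, the standard error used above belongs to the 3-month ART re-engagement difference. The planned model also draws on sexual and injecting behaviour, so the shares are illustrations. This also stands.

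A reader might infer more than the documents support:

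- *That the probability will be wrong by tens of points.* At an estimated 22 points the excess is only 0.2 to 3.3 points.
- *That the shares in step 3 describe the true effect.* They describe the estimate on which sampling is centred. Averaged over possible pilot results, Φ(−d/(√2 × 0.1195)) gives about 10% at a true 22 points and 28% at a true 10.
- *That the error peaks when the pilot shows little effect.* It is larger still for a harmful estimate.

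**Conclusion.** The point holds. Applied as written, the rule counts dominated runs as cost-effective; read narrowly, it leaves them unclassified and the reported proportion undefined. The direction of the error is certain: the probability can only be too high, and the 90% thresholds built on it too lenient.

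The size cannot be fixed from the documents. It equals the share of dominated runs, which under the assumptions in step 3 runs from negligible, if the pilot estimates the planned 22 points with little clustering, to half of all runs at a null estimate. The shift in the 90% thresholds ranges from nil to several points of effect, depending on cost inputs that the documents do not state.

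The consequence is confined to the sampled-input economic analysis under Aim 3. The point-estimate model is affected only if its own estimate shows QALYs lost. The clinical outcomes and the feasibility criterion are untouched.

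**What to change.** Replace the ratio test for individual runs with one sentence: a run is cost-effective only if willingness to pay × QALYs saved − net incremental cost is above zero. Use the same rule in the search for 90% conditions.

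An acceptable alternative is to keep the ratio and add quadrant rules under which runs with higher net cost and fewer QALYs count as not cost-effective. In this model the two give the same answer: with a positive intervention cost, and treatment cost and QALYs both tied to infections, a run cannot save money while losing QALYs. Net benefit has the advantage of covering that case too if the model changes, since the present cost-saving label ignores QALYs.

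Reporting over a range of willingness-to-pay values is useful but optional. The change costs one sentence in the plan; the model runs and data stay the same.

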The ICF will be read aloud to each eligible participant by the Interviewer. All questions that respondents may have will be adequately clarified and explained to them. Potential participants will be informed that their participation in the intervention is completely voluntary and that they have a right to withdraw their consent forms and stop their participation in the study at any time. Refusal or withdrawal from the study at any time will have no effect on the participant's access to health facilities or HIV-related care and treatment. Participants will be informed that any information that they disclose during the course of the study will be considered confidential (i.e., no personal identifiers will be used and only aggregated information across all participants will be reported). Participants will have the potential risks and benefits of the study explained to them as well. For all candidates, understanding of the essential parts of the document will be assured by asking questions to verify their knowledge of the study procedures. If a candidate agrees to participate in the study, the candidate, or a witness if a candidate is illiterate, will document provision of informed consent by signing on the consent form. Unsigned copy of consent forms will be offered to the participants.

Potential risks

Participation in HIV care and treatment in Ukraine is not associated with any punitive or social risks with the exception of common stigma. This study does not increase the risk of stigma associated with drug use or HIV for participants.

Protection Against Risks

Participation in the study is completely voluntary and confidential. The unique identifier code, linking all study records is based on information provided by participants verbally, and no documents are requested. It is not possible to identify a person using this code. Contact information will be requested to allow invitation for follow-up assessments, and this information will be kept strictly confidential (see below). Mobile phone numbers in Ukraine in most cases are not personally identifiable information, because prepaid numbers are not linked to any contract or personal registration data.

The study personnel will explain to participants that the information collected in the study may be accessed by the law enforcement entities only in case of an individualized request with regard to an open criminal case.

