As part of the informed consent procedure, all potential participants will be instructed that they do not have to disclose personal information which they are uncomfortable sharing and that they can withdraw from the study at any time.

Participants will receive names and contact information of the organizations conducting the study, as well as other study team members, on their copy of the ICF. It will be explained to the participant that they may contact anyone on the list if they have any questions or comments regarding the study, if

they suffered in any way due to their participation/failure to participate in the study. The participants will be informed that they may refuse to answer any questions that make them feel uncomfortable and that participation in the intervention is voluntary. Absolutely no information on any participants of the study will be given to other participants.

To minimize psychological risk, the recruitment into the study will be done by a trained social worker, and interview will be conducted by a trained interviewer. The interviews will be carried out face-to-face and there will be no additional persons in the room during the interview except the interviewer and respondent. Study staff will also be equipped to refer participants who need additional counseling and assistance to community resources, including referrals for HIV care and treatment.

Compensation

Participants will be compensated for their time and effort in this study, and/or be reimbursed for travel to study visits and time away from work. The compensation will be 400 UAH for each fully completed questionnaire (at baseline, 6 and 12 months), which will make 1200 UAH total if all three are completed. The compensation will be provided after each interview. This information is also specified in the ICF.

Confidentiality

All study-related information will be stored securely at the study sites and in the main office. All participant information will be stored in locked file cabinets in areas with access limited to study staff. All laboratory specimens, reports, and study data-collection, process and administrative forms will be identified by a coded number to maintain participant confidentiality. All records that contain names or other personal identifiers, such as locator forms and informed consent forms, will be stored with restricted access according to local SOP. All local databases will be secured with password-protected access systems.

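### Survey payment requires a fully completed questionnaire, which on its plain wording conflicts with the right to refuse questions and makes no exception for an interrupted interview

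*Combined protocol and SAP*

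**What the plan says.** The payment rule is in Human subjects, Quantitative data collection, Compensation: "The compensation will be 400 UAH for each fully completed questionnaire (at baseline, 6 and 12 months". A participant with no incomplete questionnaire would receive 1,200 UAH in all. On timing, it adds that "The compensation will be provided after each interview". The purpose is given at the start of the same section: "Participants will be compensated for their time and effort in this study, and/or be reimbursed for travel to study visits and time away from work". It also says that these terms appear in the consent form.

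The rights are set out in the sections just before. Under Protection Against Risks, participants are told that "they do not have to disclose personal information which they are uncomfortable sharing and that they can withdraw from the study at any time", and again that "they may refuse to answer any questions that make them feel uncomfortable". Under Informed Consent they have the right to "stop their participation in the study at any time".

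The interruption arises under Adverse events (including suicide risk). A positive response to PHQ-9 item 9 leads to one additional question. If that is also answered positively, "Interviewer will escort the patient to a clinician in the clinic for a formal assessment of suicide risk". Participants with a plan are taken to a psychiatric hospital and may be held there for up to 72 hours. The section is silent on what then happens to the questionnaire or the payment.

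For the in-depth interviews, the Compensation section under Qualitative data collection pays 300 UAH for the participant's time, with no completion condition.

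**The concern.** A consent process that grants a right and a payment rule that appears to charge for using it pull in opposite directions. The survey covers drug use, depression, stigma and risk behaviour, which are the topics on which a participant is most likely to want to decline an item. If declining costs the payment, some participants may give an answer they would otherwise have withheld, and it may be a less accurate one.

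The rule also meets the suicide-risk procedure without any provision for it. A participant who is escorted out, or transferred off site, may not reach the end of the form. On the plain wording that interview is unpaid, although the participant attended and gave time and effort.

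What is at stake is fair treatment of participants, disclosure on the safety questions, and the quality of the self-reported data. Those data supply the secondary outcomes. The syringe-sharing and intercourse items also supply the transmission parameters for the cost-threshold analysis (Statistical Analysis and Feasibility Assessment; Specific Aim 3b).

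**Working it through.** **Inputs.** From Compensation (quantitative): 400 UAH per questionnaire, three time points, stated total 1,200 UAH. From Sample size: 160 participants.

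**1. The plan's own figure.** 3 × 400 = 1,200 UAH. This reproduces the stated total.

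**2. What the literal rule costs a participant.** If full completion means that every item is answered, payment is 1,200 − 400 × (number of incomplete questionnaires):

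- one incomplete: 800 UAH, a loss of 400/1,200 = 33%
- two incomplete: 400 UAH, a loss of 800/1,200 = 67%
- three incomplete: 0 UAH, a loss of 100%

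If full completion means only that the end of the form is reached, with refusals recorded, skipping items costs nothing. The visible text does not define the term or describe partial payment. The Recruitment Log (Appendix 2) does list an incomplete visit as a possible result, so the plan foresees the event without saying how it is paid.

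**3. Rule against stated purpose.** The payment is said to be for time, effort and/or travel. A participant who attends, declines two items and finishes has given all of these. The completion condition therefore does not follow from the purpose. The sentence on paying after each interview settles timing only and does not remove the condition.

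**4. Survey against in-depth interview.** The in-depth interviews are paid without a completion condition, and Protection Against Loss of Confidentiality says participants may leave them unfinished if distressed. The survey, which carries the PHQ-9, substance-use and risk-behaviour items, is the one conditioned on completion.

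**5. Path to an interrupted interview.** Three steps are needed: a positive item 9, then a positive additional question (escort), then a plan (emergency transfer). Item 9 alone interrupts nothing. Loss of payment is most plausible at the third step, where finishing the same day is unlikely if items remain. At the second step it depends on where the PHQ-9 sits in the questionnaire and whether the interview resumes. Neither is stated.

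**6. Cost ceiling of a change.** 160 × 3 = 480 planned interviews, and 480 × 400 = 192,000 UAH. The current rule already implies this sum if everyone completes everything, so paying for each interview begun cannot exceed it.

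**7. Size of any bias.** This would need the frequency of refused items, of positive answers to the additional question and of interrupted interviews. The documents give none of these, so no figure is computed.

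**The case against.** The strongest reply is that the two statements can be read together: a questionnaire on which refusals are recorded is complete once the end is reached, and so there is no conflict. That reading is available. But the protocol does not state it, and the wording used attaches payment to full completion without qualification. The consent form and the consent procedure might define the term; the consent pages are not in the material reviewed, so this cannot be checked. It is also true that the assurance attached to refusal and withdrawal concerns access to care and says nothing about payment. That weakens the argument from the right to stop, but not the argument from the right to refuse items.

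A reader might infer more than the text supports. Four such readings should be set aside:

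- **That escorted participants lose their payment.** The adverse-events section does not say that the interview ends, that it cannot resume, or that payment is withheld. This is a gap, not a stated penalty.
- **That the rule makes the suicide screen less sensitive.** Participants would have to expect that disclosure stops the interview and forfeits the money. The documents do not say they are told this, and item 9 alone does not trigger the escort.
- **That this is the study's only check on suicide risk.** The Acuity Tool covers mental health at the intervention sites, and its items are not shown.
- **That a participant escorted at baseline has no reason to return.** Payment is per questionnaire, so 800 of the 1,200 UAH would still be available at 6 and 12 months.

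A further objection is that paying for mere attendance would reward someone who leaves at once. That is fair, and is met by requiring that the interview has begun.

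**Conclusion.** The point stands as a conflict on the plain wording between the payment condition and both the right to refuse and the stated purpose of the payment, together with the lack of any provision for an interrupted interview. For the participant, the size is 400 of 1,200 UAH, one third, for each questionnaire judged incomplete. This assumes that full completion means every item answered, or, for an interrupted interview, that the form is not finished later.

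Any effect on disclosure is possible and undocumented, and its size cannot be computed from the documents. It would fall on the suicide-risk questions, the survey-based secondary outcomes and the behavioural inputs to the cost model. The primary outcomes are taken from the medical information system (Data Collection) and are not directly affected. The payment rule is not stated to differ by arm. The change is worth making because it is cheap and removes an avoidable inconsistency.

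**What to change.** In the quantitative Compensation section and in the consent form, replace the completion condition with payment of 400 UAH for each interview attended and begun. Add two statements: refused questions do not reduce the payment; and an interview interrupted for the suicide-risk assessment is paid and may be resumed later. Explain this to participants before the baseline interview. The suicide-risk procedure itself does not change.

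The cost is one clause and two sentences in the protocol and consent form, plus some payments for partial questionnaires. The maximum stays at 1,200 UAH per participant.
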